**Exclusion Criteria:**

- 1) Subjects less than 18 years of age
- 2) A lymphocyte doubling time of < 3 months, or other clinical or laboratory signs indicating that a treatment delay of 2 months or longer (due to heavy water labeling and resting period) would result in a significant progression of the disease and be detrimental to the subject, as determined by the treating physician
- 3) Any prior treatment for CLL including chemotherapy, chemoimmunotherapy, monoclonal antibody therapy, radiotherapy, or high-dose corticosteroid therapy (Prednisone > 60 mg daily or equivalent), or immunotherapy prior to enrollment or concurrent with this trial.
- 4) Concomitant use of agents that have been described to affect the biology and/or proliferation rate of CLL cells such as: PDE-inhibitors (e.g., sildenafil, theophylline), immunosuppressive agents (e.g., prednisone, cyclosporin-A, rapamycin), green tea extract, itraconazole, ketoconazole, clarithromycin, bupropion, and Cox-2 inhibitors
- 5) Investigational agent received within 30 days prior to the first dose of study drug. If received any investigational agent prior to this time point, drug-related toxicities must have recovered to Grade 1 or less prior to first dose of study drug.
- 6) Systemic fungal, bacterial, viral, or other infection not controlled (defined as exhibiting ongoing signs/symptoms related to the infection and without improvement, despite appropriate antibiotics or other treatment).
- 7) Subjects with uncontrolled autoimmune hemolytic anemia (AIHA) or autoimmune thrombocytopenia (ITP)
- 8) Any other severe concurrent disease, or have a history of serious organ dysfunction or disease involving the heart, kidney, liver or other organ system that may place the subject at undue risk to undergo therapy with PCI-32765.
- 9) Any serious medical condition, laboratory abnormality, or psychiatric illness that places the subject at unacceptable risk if he/she were to participate in the study.
- 10) History of intracranial hemorrhage or stroke within 6 months prior to the study
- 11) Evidence of bleeding diathesis or coagulopathy
- 12) Major surgical procedure, open biopsy, or significant traumatic injury, within 28 days prior to Day 1, anticipation of need for major surgical procedure during the course of the study. (Minor surgical procedures, fine needle aspirations or core biopsies within 7 days prior to Day 1. Bone marrow aspiration +/- biopsy is allowed).
- 13) Serious, non-healing wound, ulcer, or bone fracture.
- 14) Subjects receiving anticoagulation (for example heparin, Coumadin, low-molecular-weight heparin (LMWH, such as Lovenox), and anti-platelet drugs (except for low-dose aspirin) will be ineligible to participate in this study. Subjects who recently received drugs for anticoagulation must be off those medications for at least 7 days prior to start of the study.
- 15) Subjects who are known to be anemic, with hemoglobin <8.0g/dl.
- 16) Weight less than 110 pounds
- 17) PCI-32765 is contraindicated in subjects with clinically significant hypersensitivity to any of the compound's structural components.

- 18) Subjects who are known to be infected with HIV, or have signs of active Hepatitis B or Hepatitis C
- 19) Biliary obstruction, acute hepatitis, severe liver failure, or severely impaired renal function

## 7.0 Pretreatment evaluation

Pretreatment evaluation will include a physical examination including vital signs, ECOG/WHO performance status, height and weight, and recording of concurrent medications, and will be done within 30 days prior to day 1 (See Appendix A).

Clinical laboratory evaluation will involve serum chemistries, including sodium, potassium, calcium, magnesium, phosphorus, BUN, creatinine, glucose, albumin, total protein, alkaline phosphatase, total bilirubin, ALT, uric acid, and Beta-2-microglobulin levels. Hematology studies will include complete blood count (CBC) with differential and peripheral blood lymphocyte subset analysis, immunoglobulin levels (within 30 days prior to day 1), and coagulation studies (Prothrombin Time/PT; Partial Thromboplastin Time/PTT; and International Normalized Ratio/ INR) within 30 days prior to day 1. Flow cytometry assessment for peripheral CLL cells (CLL panel) and lymphocyte subpopulations (CD3, CD4, CD8, CD19, CD16/56 cells, 30 days prior to day 1).

Bone marrow aspiration and biopsy will be obtained within one month of day 1 of the study, and again after 3, 6, and 12 cycles (+/- 1 month), only bone marrow aspirations (no biopsy) will be done during follow-up evaluations after 3, 6, and 12 cycles) after initiating PCI-32765 therapy. The screening bone marrow will be evaluated by flow cytometry for clonality and for *IGHV* mutation studies (unless known), CD38 expression, ZAP-70 expression, and cytogenetic and genomic abnormalities by FISH. Follow-up bone marrow tests after 3, 6, and 12 cycles (+/- 1 month) will evaluate morphology (bone marrow lymphocyte quantification), and quantification of CLL cells by flow cytometry, including minimal residual disease assessment by flow cytometry. Electrocardiogram (within one month from registration) will be required. We will not require additional ECG monitoring during this study. As of April 6, 2012, 408 subjects have been treated with ibrutinib in 8 clinical studies. The cardiovascular safety of ibrutinib was evaluated by monitoring of adverse events in all studies; in addition, a formal ECG monitoring was performed in 2 studies (PCYC-04753 & PCYC-1102-CA). To date there is no evidence of ECG morphological changes or prolongation of QTc in patients treated with ibrutinib. The most common cardiovascular adverse events reported across the studies were atrial fibrillation (n=17), tachycardia (n=7), sinus tachycardia (n=4) and sinus bradycardia (n=3). Events of Grade 3 or greater severity included only atrial fibrillation (n=6), supraventricular tachycardia (n=2) and tachycardia (n=1). These findings are consistent with expectations in elderly population of subjects many of whom have known cardiovascular disease at baseline. Because of these data we will not request follow-up ECGs. Subjects also will undergo CT scans of the chest, abdomen, and pelvis after 3 or 6 cycles (+/- 1 month) and after 12 cycles (+/- 1 month) of PCI-32765 therapy. Anti-coagulated blood sample (50ml) and coagulated blood sample (10ml) for baseline H2O studies on the day of study initiation (Day 1).

## **8.0 Treatment Plan**

### **8.1 Heavy Water Protocol: Labeling phase.**

After enrollment and a baseline blood draw (60ml), subjects will start to consume heavy water ( $^2\text{H}_2\text{O}$ ). Subjects will be given 50 mL of 70%  $^2\text{H}_2\text{O}$  3 times a day for the first 5 days followed by 60ml daily for a total of 4 weeks (labeling phase). Lightheadedness or dizziness may occur for some subjects (~15%) with the initial doses; therefore subjects will be given their first dose in clinic and asked to avoid driving or performing potentially hazardous activities for one hour. If such symptoms occur, they usually abate within 2-3 hours. Subjects will then be given individual doses of  $^2\text{H}_2\text{O}$  to consume at home; after the 5-day loading period, a 60 mL maintenance dose of  $^2\text{H}_2\text{O}$  will be drunk at bedtime to obviate any problems with dizziness. Compliance with  $^2\text{H}_2\text{O}$  ingestion will be documented using a heavy water ingestion diary (intake logs). Unused  $^2\text{H}_2\text{O}$  will be returned for disposal.

Subjects will be seen at day 1 (+/- 3 days), day 14 (+/- 3 days), and day 28 (+/- 3 days) after beginning  $^2\text{H}_2\text{O}$  ingestion for follow-up visits with clinical and laboratory assessment, which will include determining if there have been any problems with  $^2\text{H}_2\text{O}$  ingestion, analysis and discussion of intake logs, and blood sampling (60ml) for CLL cell kinetic measurements (heavy water testing).

### **8.2 Heavy Water Protocol: Resting phase.**

At the end of the 4th week, subjects will stop drinking  $^2\text{H}_2\text{O}$  (washout phase) and be followed for 6-12 weeks until beginning treatment with PCI-32765. During the period until initiation of therapy, subjects will be seen every 2 weeks (+/- 3 days) for follow-up visits with clinical and laboratory assessment. Blood will be drawn at the same time every 2 weeks (+/- 3 days), to determine a disappearance rate (death plus re-distribution into solid tissue) of CLL cells containing  $^2\text{H}$ -labeled DNA. Only those subjects that have not imbibed  $^2\text{H}_2\text{O}$  for at least 6 weeks from the end of the labeling period until starting on treatment with PCI-32765 or those patients who have not imbibed heavy water for less than 6 weeks and have received study PI approval will be included in further  $^2\text{H}_2\text{O}$  kinetic studies, although they will receive PCI-32765 as a part of the response to therapy studies. After start of treatment with PCI-32765, there will be blood sampling (60ml) for CLL cell kinetic measurements (heavy water testing) on days 1 (+/- 3 days), 3 (+/- 1 day), and then at week 2 (+/- 3 days) and every 2 weeks (+/- 3 days) thereafter for a period of at least equal in duration to that of the initial  $^2\text{H}_2\text{O}$  washout phase (6 to 12 weeks). Patients will continue to return to clinic each month for blood drawing (60ml). Data obtained from these blood samples will permit a determination of CLL birth rate as well as a slope of labeled cell emergence from solid tissue into the peripheral blood.

### **8.3 Treatment with PCI-32765**

PCI-32765 will be administered with 8 ounces (~240mL) of water at a dose of 420 mg (3 x 140mg capsules) orally once daily and will be continued daily. A PCI-32765 dose of 420 MG PO once daily is based on the experience in Phase 1 and Phase 2 trials which established this dose and schedule to be adequate to induce BTK target occupancy (see

Advani et al, JCO 2012). 420 mg is the dose used in all of the CLL/SLL trials to date. Each dose of PCI-32765 should be taken at least 30 minutes before eating and at least 2 hours after a meal at approximately the same time each day. Subjects will be instructed to avoid grapefruit juice due to CYP450 3A4 inhibition. Compliance with PCI-32765 ingestion will be documented using a diary. Treatment duration will be 12 cycles, with each cycle consisting of 28 days. Response will be evaluated after 3, 6 and 12 cycles. It will be possible for subjects to continue taking the drug beyond 12 cycles if there is a significant benefit such as an ongoing PR or CR. Unused PCI-32765 will be returned for disposal per institutional policy.

#### **8.4 Special Handling Instructions**

Allopurinol at the dose of 300mg daily will be given during the first one to two weeks of treatment as standard tumor lysis prophylaxis.

#### **8.5 Concomitant Medication**

Subjects receiving anticoagulation (for example heparin, Coumadin, low-molecular-weight heparin (LMWH, such as Lovenox), and anti-platelet drugs (except for low-dose aspirin) will be ineligible to participate in this study. Subjects who recently received drugs for anticoagulation must be off those medications for at least 7 days prior to start of the study.

#### **8.6 Guideline for Use of CYP Inhibiting Drugs**

PCI-32765 is metabolized by CYP3A4/5 and CYP2D6. Alternatives to strong CYP3A4/5 inhibitors (such as clarithromycin, ketoconazole, itraconazole, nefazodone, and ritonavir) and strong CYP2D6 inhibitors (such as bupropion, fluoxetine, paroxetine, and quinidine) should be sought if possible.

If no alternative treatment is available, strong CYP3A4/5 and CYP2D6 inhibitors should be used with caution; patients should be closely monitored for potential toxicities with temporary interruption of PCI-32765 as appropriate.

A comprehensive list of cytochrome P450 isoenzymes and CYP3A4/5 and CYP2D6 inhibitors, inducers, and substrates can be found at <http://medicine.iupui.edu/flockhart>. This website is continually revised and should be checked frequently for updates.

#### **8.7 Concomitant Use of QT Prolonging Agents**

During the course of study drug treatment medications known to cause Torsades des Pointes should be avoided. Medications known to cause QT prolongation may be used with caution.

#### **8.8 Concomitant Use of Antiplatelet Agents and Anticoagulants**

Laboratory studies have shown that, *in vitro*, PCI-32765 can prevent platelets from aggregating normally; the clinical significance of this finding is unknown at this time. While serious bleeding has been uncommon in patients treated to date, it is possible that treatment with the study drug could increase the risk of bruising or bleeding, particularly in subjects receiving other antiplatelet agents or anticoagulants.

Subjects receiving antiplatelet agents in conjunction with PCI-32765 should be observed closely for any signs of bleeding or bruising, and PCI-32765 should be withheld in the event of any bleeding events.

Subjects requiring the initiation of anticoagulation with warfarin or related agents during the course of the study should have treatment with PCI-32765 held, and PCI-32765 should not be restarted until subjects are stably anticoagulated. During the co-administration of PCI-32765 and anticoagulant therapy, the INR should be monitored carefully and subjects should be observed closely for signs and symptoms of bleeding.

### **8.9 Sample Collections for H-DNA-labeled Leukemic Cells during PCI-32765 Treatment Phase**

After beginning PCI-32765 therapy, subjects will be seen for follow-up visits including blood draws (60ml) at day 1 (+/- 3 days), day 3 (+/- 1 day), week 2 (+/- 3 days), and every 2 weeks (+/- 3 days) thereafter for a period at least equal in duration to that of the initial H2O washout phase of 6 to 12 weeks. At these visits, clinical and laboratory assessment, which will include blood sampling (60ml) for H2O kinetic measurements, will be made. Subjects will continue to return or be seen by a local physician or clinical laboratory each month (+/- 3 days) for an additional 3 months for blood drawing (60ml). Data obtained from these blood samples will permit a determination of the slope and rate of the appearance of previously labeled CLL cells in the blood, and the slope and rate of the disappearance of labeled cells from the blood. If re-circulation to solid tissues is inhibited by PCI-32765 therapy, the disappearance rate will represent primarily the death rate of leukemic cells *in vivo*. Because during the treatment period, H2O will not be available to label newly-born cells, any cells containing H-labeled DNA will represent cells labeled during the initial period of H2O consumption and retained *in situ*. The kinetic measurements of the entire CLL clone will be compared with those of intracлонаl fractions from the same samples, defined by the reciprocal differences in CXCR4/CD5 surface membrane densities; this approach is described in the published study by Calissano et al. (Mol Med 2011;17: 1374-1382, 2011). In addition, these fractions will be analyzed for:

1. Phenotype and numerical changes of B and T cells and myeloid cells within these fractions, pre- and post-ibrutinib therapy
2. Gene expression profiles of cells within these fractions, pre- and post-ibrutinib therapy
3. DNA methylation profiles of cells within these fractions, pre- and post-ibrutinib therapy.

4. Response to BCR and other signals of cells within these fractions, pre- and post-ibrutinib therapy, using western blots on phosphoproteins/ibrutinib occupancy
5. Differences in engraftment and growth capacities of CLL B and T cells in NSG mice, unseparated or within these fractions, pre- and post-ibrutinib therapy

All data will be correlated with the kinetic data of the clone and its CXCR4/CD5 subsets in order to better characterize CLL cell subpopulations that are affected by PCI-32765 therapy and that account for CLL cell mobilization and/or proliferation. These additional analyses will be done at [name] site, in collaboration with [name] and his colleagues at MD Anderson Cancer Center.

#### **8.10 Outside Physician Participation during Treatment**

1. MDACC Physician communication with the outside physician is required prior to the patient returning to the local physician. This will be documented in the patient record
2. A letter to the local physician outlining the patient's participation in a clinical trial will request local physician agreement to supervise the patient's care (see Appendix H)
3. Protocol required evaluations outside MDACC will be documented by telephone, fax or e-mail. Fax and/or e-mail will be dated and signed by the MDACC physician, indicating that they have reviewed it.
4. Changes in drug dose and/or schedule must be discussed with and approved by the MDACC physician investigator, or their representative prior to initiation, and will be documented in the patient record.
5. A copy of the informed consent, protocol abstract, treatment schema and evaluation during treatment will be provided to the local physician.
6. Documentation to be provided by the local physician will include progress notes, reports of protocol required laboratory and diagnostic studies and documentation of any hospitalizations.
7. The home physician will be requested to report to the MDACC physician investigator all life threatening events within 24 hours of documented occurrence.
8. Patients will return to MDACC every month for the first 3 months of starting treatment with PCI-32765, and then every 3 cycles for evaluation (every 6 months after cycle 36)

#### **9.0 Special Instructions about Heavy Water Ingestion:**

##### **Related to heavy water**

“Heavy water” is similar to “regular water” in taste, smell, and color. There are no known major harmful effects of heavy water when consumed in the amounts given in this study. Minor side effects include nausea, dizziness, lightheadedness, and vertigo. Participants will be advised to avoid performing activities such as driving, operating machinery, and exercise that could potentially compromise their safety immediately after drinking the heavy water. They should wait at least 60 minutes before resuming any strenuous activities. Unused  $^2\text{H}_2\text{O}$  will be returned for disposal.

### **Special Instructions Related to contraception**

#### **Heavy Water:**

Even though no pregnant women will be enrolled in this study, deuteriated compounds including deuteriated vitamin E, deuteriated nicotine, and deuteriated water have been given to pregnant women to study the physiology of pregnancy and no ill effects to mother or fetus have been observed.

#### **PCI-32765:**

The potential effects of PCI-32765 on a developing fetus have not been determined in animals or humans.

Therefore, if a woman of childbearing potential is enrolled in this study or a man with a partner who has childbearing potential, the couple will use two forms of birth control for the entire time of the study and 30 days after finishing study. Conception control should include a hormonal method (birth control pill, etc.), and a double-barrier methods (condoms with spermicidal, sponge with spermicidal, or diaphragm with spermicidal), or abstinence (not having sex) will be practiced.

## **10.0 Evaluation during Study**

- **Clinic visits, end of treatment visit**

Each clinic visit will include vital signs and a physical exam. Physical examinations should include height (screening only) and weight, examination of the skin, eyes (with specific questions focused on ocular symptoms), ears, nose, throat, lungs, heart, abdomen, extremities, and lymphatic system. The examination should also include inquiry of ocular symptoms and subjects should be referred to an ophthalmologist for a formal examination if any Grade > 2 symptoms are reported. After beginning PCI-32765 therapy, subjects will be seen for follow-up visits including blood draws (60ml) on days 1 (+/- 3 days), 3 (+/- 1 day), and then at week 2 (+/- 3 days), and every 2 weeks (+/- 3 days) thereafter for a period at least equal in duration to that of the initial 2H2O washout phase of 6 to 12 weeks. Subjects will return to clinic or will be seen by a local physician each month (+/- 3 days) for an additional 3 months for follow-up visits with clinical and laboratory assessment, including vital signs and physical exam, and laboratory workup, including hematology and clinical chemistry evaluations and then every 3 months (+/- 3 days) until the end of 12 cycles. If subjects stay on the study past 12 cycles, they will return for clinic visits for clinical assessment, including vital signs and physical exam, and laboratory workup, including hematology and clinical chemistry evaluations, every 3 months (+/- 1 month) for cycles 13 through 36, and every 6 months (+/- 1 month) thereafter. For patients that discontinue therapy with PCI-32765, an end of study visit at MD Anderson will be required. Patients will be followed for at least 2 months (+/- 1 month) after the last dose of PCI-32765 for assessment of adverse events. This will be done in a Leukemia Clinic visit that will be scheduled to occur at 1 month (+/- 10 days) after the last dose of PCI-32765.

- **Hematology and serum chemistry**

CBCs (white blood cell, hemoglobin, platelets and differential) will be monitored on days 1, 14, and 28 (+/- 3 days) and then every 4 weeks (+/- 3 days) thereafter. Serum chemistry including basic metabolic profile (sodium, potassium, chloride, CO2, BUN, creatinine and glucose) will be monitored once weekly (+/- 3 days) for the first 4 weeks and then once every 4 weeks (+/- 3 days) thereafter until the end of cycle 12. If subjects stay in the study past 12 cycles, they will have these laboratory tests (hematology and clinical chemistry) done every 3 months (+/- 1 month) for cycles 13 through 36, and every 6 months (+/- 1 month) thereafter during their clinic visit.

PT, PTT, and INR will be monitored after cycles 3 and 12 (+/- 1 week) and if subjects stay on the study past 12 cycles, once every 12 cycles (+/- 1 month).

- **Bone marrow testing, beta-2-microglobulin, lymphocyte subset, immunoglobulin levels**

Bone marrow testing will be done by flow cytometry after 3 (+/- 1 month), 6 (+/- 1 month), and 12 cycles (+/- 1 month) and if subjects stay in the study past 12 cycles, once every 12 cycles (+/- 1 month). Beta-2 microglobulin and immunoglobulin levels will be assessed at screening and at the timepoints specified in the study calendar (see calendar of events at the end of the protocol).

- **CT scans of the chest, abdomen, and pelvis**

These will be performed within 30 days before starting Heavy Water, and then after 3 or 6 cycles, and after 12 cycles. All other scans are at the treating physician's discretion.

- **Research Testing as an Optional Procedure**

Patient samples (blood cells, DNA, RNA) will be analyzed by colleagues at the Dana-Farber Cancer Institute (DFCI), Boston ([name] and associates) for gene mutations within the CLL cells in patients responding or not responding to therapy with PCI-32765. These tests will allow us to determine why some CLL cells persist during therapy with PCI-32765 and why some patients have suboptimal responses or no response to PCI-32765. No additional blood draws will be necessary for these tests.

Blood samples will be analyzed by [name] [name] (Department of Lymphoma and Myeloma, MD Anderson) for changes in gene expression in CLL cells during therapy with PCI-32765. For these studies, one additional tube of blood (approximately 1 tablespoon per time point) will be collected on cycle 1, week 1, day 1 (+/- 3 days) before the start of PCI-32765, and day 3 (+/- 1 day), and on week 4 (+/- 3 days), and week 12 (+/- 3 days), during therapy with PCI-32765.

Finally, a sputum sample will be collected on day 1 of week 1 (+/- 3 days) during follow-up which will serve as a control for the genetic testing of the leukemia cells.

Samples collected will be stored at [name] laboratory and then sent to the Dana-Farber Cancer Institute

- **Confidentiality**

All patient-identifying information will be removed from all samples before being sent to DFCI and [name] laboratory and will only be available to the PI at MD Anderson, [name].

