**4.0 Objectives**

The primary objective is to assess the impact of the Bruton's tyrosine kinase (Btk) inhibitor PCI-32765 on leukemia cell trafficking and death using heavy water ( $^2\text{H}_2\text{O}$ ) labeling of newly-born malignant cells in subjects with Chronic Lymphocytic Leukemia (CLL) and Small Lymphocytic Lymphoma (SLL).

The secondary objective is to determine the percent of recently born versus older leukemia cells mobilized into the blood by PCI-32765 treatment.

The tertiary objective is to compare the kinetic biomarker measurements in CLL subjects to other established prognostic tests and response to therapy with PCI-32765.

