**Treatment Plan PCI-32765**

Evaluation or Procedure	Cycle 1 (weeks 1-4)			Cycle 2 (weeks 6-8)		Cycle 3 through 6 (weeks 10-20)		Cycle 6, 9	Cycle 12	Cycles 13 through 36, and after cycle 36 (see footnote "j")	
	Week 1		Week 2	Week 4	Week 6	Week 8	Week 10	Week 12 16, 20	Week 24, 36		Week 48
Clinical Assessments	Day 1 (+/-3 days)	Day 3 (+/-1 Day)									
Follow-up Visits a with physical evaluation a, e, i	X	X		X	X	X	X	X	X	X	X
Serum Chemistry e and Hematology d	X			X	X	X	X		X		X
PT/PTT/INR p								X (only week 12)		X	X
Blood Sample for heavy water testing	X	X		X q	X q	X q	X q	X q	X q (only week 12)		
CT Scans s								X (only week 12)	X	X	X
PCI-32765 (3 x 140 mg =420 mg) m	X	X		X	X	X	X	X	X	X	X
Allopurinol 300mg n	X	X		X							
Immunoglobulin Levels and Lymphocyte Subpopulation f	X								X (only week 12)	X	X
Bone marrow aspiration t									X (only week 12)	X	X
Blood draw for research testing u	X	X			X				X (only week 12)		
Sputum Sample v	X										

Schedule of Events for  
Heavy Water and PCI-32765  
07-03-2013

- a. Including vital signs.
- b. Patients will be seen at day 1 (+/- 3 days), day 14 (+/- 3 days), and day 28 (+/- 3 days) after beginning  $^2\text{H}_2\text{O}$  ingestion for follow-up visits with clinical and laboratory assessment, which will include determining if there have been any problems with the ingestion of heavy water and assessment of other adverse events, assessment of concomitant medications, analysis, and discussion of intake logs and blood sampling (60ml) for  $^2\text{H}_2\text{O}$  kinetic measurements. CBCs (white blood cell, hemoglobin, platelets and differential) will be monitored on days 1, 14, 28 (+/- 3 days), and then every 4 weeks (+/- 3 days) thereafter.
- c. Prothrombin Time/PT; Partial Thromboplastin Time/PTT, and International Normalized Ratio/INR.
- d. Hematology and serum chemistry: complete blood counts (white blood cell, hemoglobin, platelets and differential) will be monitored on days 1, 14, 28 (+/- 3 days) for the first four weeks and then every four weeks thereafter.
- e. Includes sodium, potassium, calcium, magnesium, phosphorus, BUN, creatinine, glucose, albumin, total protein, alkaline phosphatase, total bilirubin, ALT, and uric acid.

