- q. Blood draws (60ml) at week 2 (+/- 3 days) and every 2 weeks (+/- 3 days) thereafter for a period of at least equal in duration to that of the initial  $^2\text{H}_2\text{O}$  washout phase (6 to 12 weeks) for  $^2\text{H}_2\text{O}$  kinetic measurements. Data obtained from these blood samples will permit a determination of the slope and rate of the appearance of previously labeled CLL cells in the blood, and the slope and rate of the disappearance of labeled cells from the blood.
- r. Anti-coagulated blood sample (50ml) and coagulated blood sample (10ml) for baseline  $^2\text{H}_2\text{O}$  studies on the day of study initiation.
- s. CT scans of the chest, abdomen, and pelvis after cycles 3 or 6, and 12. Beyond cycle 12, CT scans are at physicians discretion.
- t. Bone marrow will be evaluated by flow cytometry for clonality and for amount of CLL cell infiltration, including detection of minimal residual disease after 3, 6, and 12 cycles (+/- 1 month) of therapy with PCI-32765. Bone marrow testing at later time points is at the treating physician's discretion.
- u. Blood draws using one 2.5ml PaxGen tube will be collected in cycle 1, week 1, days 1 (+/- 3 days) and 3 (+/- 1 day), week 4 (+/- 3 days), and week 12 (+/- 3 days), for research testing.
- v. One Sputum sample will be collected on day 1 (+/- 3 days) of beginning therapy with PCI-32765 for research testing.

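### No blood count is guaranteed at the PCI-32765 day 3 and week 10 kinetic draws, and text and calendar conflict at week 6, so the size of the labelled share among mobilised cells is not secured there

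*Combined protocol and SAP*

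**What the plan says.** The secondary objective (Section 4.0) is to "determine the percent of recently born versus older leukemia cells mobilized into the blood by PCI-32765 treatment".

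On treatment, Section 8.9 sets the kinetic draws "at day 1 (+/- 3 days), day 3 (+/- 1 day), week 2 (+/- 3 days), and every 2 weeks (+/- 3 days) thereafter", for at least as long as the 6 to 12 week washout. Sections 8.2 and 10.0 give the same early draws, and footnote q of the Schedule of Events repeats the two-weekly rule.

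Complete blood counts follow a different rule. Section 10.0 says they "will be monitored on days 1, 14, and 28 (+/- 3 days) and then every 4 weeks (+/- 3 days) thereafter". Footnote d, attached to the hematology row of the PCI-32765 grid, says they "will be monitored on days 1, 14, 28 (+/- 3 days) for the first four weeks and then every four weeks thereafter". Footnote b gives the same rule in the heavy-water phase.

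The statistical section (13.0) works with LC, the observed percentage of labelled cells. It mentions no absolute count and gives no formula for the make-up of the mobilised cells.

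**The concern.** LC describes all CLL cells in the blood at a draw. The objective asks about a subset: those that the drug has moved into the blood. Inferring the subset from the whole requires the change in LC and also the growth of the blood pool. Section 2.1 expects that pool to change, since it describes rapid nodal shrinkage with a transient lymphocytosis.

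Day 3 is the only kinetic draw between treatment day 1 and week 2, so it is the draw placed to catch early mobilisation. If no count is taken with it, the plan records how the label mix shifted but not how many cells arrived. A count that was not taken cannot be recovered later, however exploratory the analysis.

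**Working it through.** **Step 1. Match kinetic draws to scheduled counts on treatment.** The grid columns were aligned using the research-draw row, which footnote u fixes at day 1, day 3, week 4 and week 12. The table was read from PDF and some rows are shifted, so the week 6 mark needs caution.

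| Kinetic draw | Count by text (Section 10.0, footnote d) | Count by grid, as extracted |
|---|---|---|
| Day 1 | yes | yes |
| Day 3 | no | no |
| Week 2 | yes | yes |
| Week 4 | yes | yes |
| Week 6 | no | yes |
| Week 8 | yes | yes |
| Week 10 | no | no |
| Week 12 | yes | yes |

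To week 12, 3 of 8 draws are unmatched by the text and 2 of 8 by the grid. If two-weekly sampling stops at week 6, the figures are 2 of 5 and 1 of 5. The grid row combines hematology with serum chemistry, but Section 10.0 also makes chemistry 4-weekly after the first four weeks, so chemistry does not explain the week 6 mark.

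**Step 2. Check whether the visit windows close the gap.**
- Week 6 covers days 39 to 45. The nearest text-rule counts cover days 25 to 31 and 53 to 59, so there is no overlap.
- Week 10 covers days 67 to 73. The nearest counts cover days 53 to 59 and 81 to 87, so there is no overlap.
- Day 3 covers days 2 to 4, which falls inside the day 1 window of +/- 3 days. But one count used for day 3 leaves day 1 without its own, and both are needed.

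**Step 3. Show what the count contributes.** Let N1 and N2 be the circulating CLL counts at two draws, with R = N2/N1. Ignoring death and return to tissue between the draws, the labelled share of the mobilised cells is

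(LC2 × N2 − LC1 × N1) / (N2 − N1) = (LC2 × R − LC1) / (R − 1) = LC2 + (LC2 − LC1) / (R − 1).

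The documents give no values for LC or R, so these are assumptions. With LC1 = 5% and LC2 = 6%:
- R = 1.2: 6 + 1/0.2 = 11%
- R = 1.5: 6 + 1/0.5 = 8%
- R = 3: 6 + 1/2 = 6.5%
- R = 5: 6 + 1/4 = 6.25%

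**Step 4. Test interpolation as a substitute.** Assume LC of 5% on day 1 and 8% on day 3, with true count ratios of 2 at day 3 and 3 at day 14. The true share at day 3 is 8 + 3/(2 − 1) = 11%.
- Linear interpolation between days 1 and 14: R = 1 + 2 × 2/13 = 1.308, and the share is 8 + 3/0.308 = 17.8% (unrounded R).
- Log-linear interpolation: R = 3^(2/13) = 1.184, and the share is 24.3%.

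Interpolation fails here because the early rise is assumed to be steep. If the true day 3 ratio were 1.3, the true share would be 8 + 3/0.3 = 18% and the linear estimate would be close. The data planned at day 3 would not show which case applies.

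**The case against.** A reader might infer that the secondary objective cannot be met. The documents do not support that.
- Section 8.9 promises clinical and laboratory assessment at every kinetic visit, including day 3. Where Section 10.0 and footnote l spell out the laboratory workup, for the later visits, it includes hematology. The 4-weekly rule could therefore be read as a minimum.
- The 60 ml sample could itself be counted, and Section 8.9 lists numerical changes within cell fractions among its analyses.
- If the count has risen, the direction is known without its size: the share lies above LC2 when LC rose and below it when LC fell.

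These points stand as possibilities. But no passage names a count at day 3, requires one on the kinetic sample, or gives time points for the fraction counts. For the day 3 and two-weekly visits, footnote l names only adverse events and concomitant medications.

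Three further readings are tempting and do not hold.
- That every other later draw lacks a count. Weeks 2 and 4 are both covered, and the grid appears to cover week 6.
- That mobilised cells carrying the same label as blood cells would defeat the objective. In that case the formula returns LC at any ratio other than 1. What is lost is the size of the mobilisation, not the percentage that the objective asks for.
- That the rest-phase gaps add to the problem. The heavy-water grid does leave weeks 6, 10 and 14 without hematology although Section 8.2 asks for two-weekly draws. But the objective concerns cells mobilised by PCI-32765, and its pre-drug reference is the treatment day 1 count, which is scheduled.

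It is also fair to say that Section 10.0 does not state which day 1 its rule counts from. Footnote d carries the rule into the treatment grid, and no reading of the rule schedules a count on treatment day 3.

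**Conclusion.** The point holds in a limited form. The plan does not guarantee a blood count at the day 3 or week 10 kinetic draws on treatment, and its text and grid conflict at week 6. To week 12, 3 of 8 on-treatment draws are unmatched by the text and 2 of 8 by the grid. At those draws LC alone does not give the size of the labelled share among mobilised cells whenever LC has changed. In the illustration the answer runs from 6.25% to 11%; most of that spread comes from the smallest ratio, and from 1.5-fold to 5-fold it is 8% to 6.25%.

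This rests on assumed LC values and ratios, on a mass balance that ignores death and return to tissue, and on the grid alignment described above. Day 3 matters most because it is the only early on-drug draw, although Section 13.0 also allows for later and multiple peaks. The statistical section's silence on a formula is part of the same gap. The amendment is worth making because a named objective depends on a cheap measurement that the calendar leaves out.

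**What to change.** 1. Reconcile Section 10.0, footnotes b and d and the PCI-32765 grid so that a blood count with differential is run from the same venipuncture at every on-treatment kinetic draw, naming day 3 and weeks 6 and 10.
2. In Section 13.0, state the formula for the labelled share of mobilised cells and its assumption of no death and no re-entry between draws.
3. A differential gives lymphocytes, not CLL cells. Declare the absolute lymphocyte count a proxy for the CLL count, or multiply it by the CLL fraction where flow cytometry is available.
4. Report the day 1 to day 3 estimate and the later estimates from the paired values.

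The cost is two extra counts per subject relative to the grid, or three relative to the text, when sampling runs to week 12. For 30 subjects that is 60 to 90 counts, on blood already being drawn and with no new visit, plus a calendar amendment. Counts at rest-phase weeks 6, 10 and 14 are optional. They would support the description of the disappearance rate, not the secondary objective.
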